- s PLA₂ sampling will be performed for all subjects on Day 1 (pre-dose and 1, 3, 6, and 9 hours post-first dose), and on Day 2, Day 3, and Day 7 (pre-dose). sPLA₂ in serum and PK samples will be processed and analyzed in a central laboratory, not at individual sites.
- PK sampling will only be performed for a total of 20 adult and pediatric subjects on Days 1 and 3, and all subjects on Day 7. Once 20 subjects have provided PK samples for Days 1 and 3, sites will be notified by the sponsor to discontinue Day 1 and 3 PK sampling. Subjects will be enrolled for PK analysis as follows: Day 1 20 subjects, pre-dose and 0.5, 1, 2, 4, 6, 8, and 12 (pre-second dose) hours; Day 3 20 subjects, pre-dose and 0.5, 1, 2, 4, 6 hours; Day 7 all subjects, pre-dose.

Figure 1 Study Schematic

- a. Because snakebite subjects are considered critically ill and will arrive in an emergency department setting, Screening, Baseline evaluation, randomization, and treatment must all take place on Study Day 1
- b. Assessments (see Schedule of Events) must be performed at the following times post-initial dose: 3 to 4 hours, 5 to 6 hours, 8 to 10 hours, 2 days (12 to 18 hours after last Day 1 measurements), 3 days (approximately 24 hours after Day 2 measurements), 7 days ± 1 day, 14 days ± 2 days, and 28 days ± 3 days
- c. The varespladib-methyl dosing for adult subjects is a 500 mg loading dose, a 250 mg dose approximately 12 hours later, then 250 mg BID for the remainder of the study period; pediatric subjects (ages 5 to < 18) will be administered doses of varespladib-methyl determined by allometric scaling, provided as 50 mg capsules, depending on age (see Section 7.3). Abbreviations: BID = twice daily; SOC = standard of care; yr = years

3		TABLE OF CONTENTS	
1	APF	PROVAL SIGNATURES	2
2	PRO	OTOCOL SUMMARY	3
	2.1	Synopsis 3	
	2.2	Schedule of Events	9
3	TAI	BLE OF CONTENTS	14
	3.1	List of In-text Tables	18
	3.2	List of In-text Figures.	18
4	LIS	Γ OF ABBREVIATIONS AND DEFINITION OF TERMS	19
5	INT	RODUCTION	20
	5.1	Background and Rationale	

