7.3 Selection of Doses in the Study

LY333013 (varespladib-methyl) is formulated in an immediate-release film-coated oval tablet at a unit dosage strength of 250 mg for oral administration. Ophirex is developing varespladib-methyl (LY333013) for oral administration for 7 days total for the treatment of venomous snakebites. LY333013 is a prodrug that is rapidly metabolized to LY315920; LY315920 is a potent inhibitor of sPLA₂ in vitro and in vivo.

This study evaluates the safety, tolerability, and efficacy of varespladib-methyl in subjects bitten by venomous snakes from diverse regions and snake genera, including (but not limited to) pit vipers (e.g., rattlesnake, copperhead), vipers (e.g., Russell's viper and saw-scaled viper), and elapids (e.g., coral snake, cobra, krait).

The proposed dosing of varespladib-methyl for adult subjects consists of an initial loading dose of 500 mg ($2 \times 250 \text{ mg}$ oral tablet) varespladib-methyl upon randomization, followed by dosing with 250 mg varespladib-methyl ($1 \times 250 \text{ mg}$ oral tablet) approximately 12 hours later, followed by BID dosing with $1 \times 250 \text{ mg}$ varespladib-methyl oral tablets for the remainder of the 7-day treatment period.

Pediatric subjects (ages 5 to < 18) will be administered doses of varespladib-methyl determined by allometric scaling, provided as 50 mg capsules, depending on age. Pediatric doses were determined based on the 250 mg BID adult dose. Median weights from the Centers for Disease Control (CDC) growth charts were used for the allometric scaling, with weights averaged for male and female pediatric subjects. Subjects 5 to < 11 years old will receive an initial loading dose of 200 mg varespladib-methyl, an additional dose of 100 mg approximately 12 hours later, followed by 100 mg BID. Subjects 11 to < 18 years old will receive a loading dose of 400 mg varespladib-methyl, an additional dose of 200 mg approximately 12 hours later, followed by 200 mg BID. Including the loading dose, subjects will receive a total of 14 doses of study medication. Dosing may occur on 7 or 8 calendar days, depending on whether the first dose of study medication is in the morning or the afternoon.

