10.2 Study Periods and Visits

10.2.1 sPLA₂ and Pharmacokinetics Sample Timing

Note that the sPLA₂ and PK sample collection will be performed with a different timing than the other assessments, as described in the Schedule of Events (Table 1).

Specifically, PK sampling will only be performed for a subset of adult and pediatric subjects on Days 1 and 3 and all subjects on Day 7 as described in Section 10.3.2.1. Subjects will be enrolled for PK analysis as follows: Day 1 - 20 subjects, pre-dose and 0.5, 1, 2, 4, 6, 8, and 12 (pre-second dose) hours; Day 3 - 20 subjects, pre-dose and 0.5, 1, 2, 4, 6 hours; Day 7 - all subjects, pre-dose. Special attention should be paid to collection of PK samples on Day 1 of this protocol.

sPLA₂ sampling will be performed for all subjects on Day 1 (pre-dose and 1, 3, 6, and 9 hours post-first dose), and on Day 2, Day 3, and Day 7 (pre-dose).

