10.3.2 Pharmacokinetics

10.3.2.1 Pharmacokinetic Analysis Methods

The concentration of varespladib-methyl in plasma will be evaluated in a subset of both adult and pediatric subjects on Days 1 and 3 and in all subjects on Day 7. PK sampling will only be performed for a total of 20 adult and pediatric subjects on Days 1 and 3, and all subjects on Day 7. Once 20 subjects have provided PK samples for Days 1 and 3, sites will be notified by the

OPX-PR-01

sponsor to discontinue Day 1 and 3 PK sampling. Efforts will be made to include at least 4 pediatric subjects from each age tier (5 to < 11, 11 to < 18 years old) in the PK analysis. PK samples will be collected on Days 1 and 3 as follows:

- Day 1 (20 adult and pediatric subjects): pre-dose and 0.5, 1, 2, 4, 6, 8, and 12 (pre-second dose) hours post-dose.
- Day 3 (20 adult and pediatric subjects): pre-dose and 0.5, 1, 2, 4, and 6 hours post-dose.
- Day 7 (all 110 subjects): pre-dose.

The PK characterization of drug concentrations for each dose to be profiled will use noncompartmental analysis (NCA). Additional details of the parameters and their calculation and evaluation is included in the Statistical Analysis Plan (SAP).

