#### **6.1.7.15. Data Adjustments/Handling/Conventions**

All collected data will be presented in listings. Data not subject to analysis according to this plan will not appear in any tables or graphs but will be included only in the data listings.

Day 1 will refer to activities that occurred at baseline through the first 12 hours after the patient receives the study drug (regardless of whether the calendar day has changed). Day 2 assessments will occur at least 12 hours and not more than 18 hours after the 8-10 hour assessment on Day 1. Thereafter, Day will refer to calendar day following the initiation of treatment (e.g., Day 28 will occur 27 days after the day on which the patient received their first dose of study drug).

*P* values will be displayed with two significant figures if the value is greater than or equal to 0.01 (eg., 0.XX) and with one significant figure is less than 0.01 (eg., 0.00X). If a *P* value less than 0.0001 occurs, it will be shown in tables as < 0.0001.

Adverse events will be coded using the latest MedDRA version thesaurus.

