## **11.      Other Planned Analysis**

## 11.1. Pharmacokinetic Analysis

Descriptive summaries of the concentration level of varespladib-methyl in plasma and sPLA2 activity at specified timepoints will be tabulated by treatment group.

By-subject concentrations of varespladib-methyl in plasma will also be presented.

The pharmacokinetic characterization of drug concentrations for each dose to be profiled will be performed using noncompartmental analysis (NCA).

The PK parameter estimates will be completed using Phoenix WinNonlin (Pharsight Corporation) software using the actual elapsed times from dose administration to sample collection. For plasma concentration data, all values below the limit of quantification (BLQ) will be set to 0 for summary statistics and graphs. For the PK parameter calculation, BLQ plasma concentrations occurring before Tmax will be set to 0, with the exception of a BLQ value occurring between two measurable concentrations, in which case it will be set to missing.

Standard PK parameters assessed will include measures of the extent of absorption using estimates of the area under the plasma concentration-time curve from time 0 to the time of the last quantifiable plasma concentration (AUC0-t), Area under the plasma concentration-time curve from time 0 to infinity (if data permits) (AUC0-inf) and rate of absorption using the maximum serum plasma concentration (Cmax), the time of Cmax (Tmax), apparent first order terminal elimination half-life (t1/2), apparent terminal phase rate constant ( $\lambda_z$ ) (if data permits). Any subject for whom the portion of the AUC extrapolated to infinity exceeds 20% of the total AUC0-inf will be excluded from the calculation of the descriptive statistics for AUC0-inf.

Other PK parameters may be derived, where appropriate, and as data permit.

For noncompartmental analysis, plasma concentrations will be listed and summarized at each time point using descriptive statistics. Descriptive statistics reported will include the arithmetic mean, SD, CV%, geometric mean, minimum, maximum, and median. Only the range and the median will be reported for Tmax and Tlast, as these are categorical parameters. The PK parameters will also be summarized by treatment using descriptive statistics.

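### The Day 7 PK and sPLA2 samples are labelled pre-dose, but on the Protocol's clock 75% of the visit window falls after the last dose, and the SAP counts Day 7 differently

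*Protocol*

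**What the plan says.** **Dosing.** Protocol 7.3 states "Including the loading dose, subjects will receive a total of 14 doses of study medication". In every age group the second dose comes about 12 h after the loading dose, with twice-daily dosing from then on. The same section allows dosing to span 7 or 8 calendar days.

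**Sampling.** Day 1 and Day 3 PK profiles are limited to 20 subjects. The Day 7 sample is taken in everyone: "Day 7 (all 110 subjects): pre-dose" (Protocol 10.3.2.1). Protocol 10.2.1 sets sPLA2 draws for all subjects at Day 1 times "and on Day 2, Day 3, and Day 7 (pre-dose". It adds that PK and sPLA2 timing differs from that of other assessments and refers to Table 1. Table 1 and its notes give no separate Day 7 window and no dose number.

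**Visit timing.** Figure 1 note b counts from the initial dose and gives the later visits as "7 days ± 1 day, 14 days ± 2 days, and 28 days ± 3 days". The Day 7 visit list (10.2.3.9) still instructs sites to continue twice-daily dosing.

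**SAP.** After Day 2, "Day will refer to calendar day following the initiation of treatment" (SAP 6.1.7.15), so Day 7 is six days after the dosing day. SAP 6.1.7.2 likewise treats anything before 144 h as before Day 7, yet fixes the Day 7 SSS at 168 h. SAP 11.1 says "plasma concentrations will be listed and summarized at each time point using descriptive statistics", with values below the quantification limit set to 0 for summaries and graphs. Actual elapsed times are used for the PK parameter estimates.

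**The concern.** A pre-dose sample needs a dose still to come. If the last dose has already been taken when the subject attends, the label is wrong and time since last dose varies with the visit date.

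This matters for two summaries. For about 90 of 110 subjects (110 − 20), in either arm, Day 7 is the only PK sample. Day 7 is also the final sPLA2 point in the between-arm curve comparison of SAP 8.3.13, which yields a p-value. Mixing samples taken before a dose with samples taken well after treatment ended could lower the Day 7 mean concentration. It could also make end-of-treatment sPLA2 inhibition look weaker, for reasons of scheduling rather than drug effect.

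**Working it through.** **Inputs.** 14 doses (Protocol 7.3); 12 h between doses (stated for the first interval as approximate, assumed for the rest); Day 7 at 7 ± 1 days after the initial dose (Figure 1 note b); Day 7 as a calendar day six days after the dosing day (SAP 6.1.7.15).

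**The plan's own figure.** 7 days × 2 per day = 14 = 1 loading dose + 13 further doses. It reproduces.

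**Time of the last dose.** (14 − 1) × 12 h = 156 h after the first.

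**Split of each 48-hour window**

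| Day 7 clock | Window | Before dose 14 | 0-12 h after it | More than 12 h after it | No dose left |
|---|---|---|---|---|---|
| Protocol, 168 ± 24 h | 144-192 h | 12 h (25%) | 12 h (25%) | 24 h (50%) | 36 h (75%) |
| SAP, about 144 ± 24 h | 120-168 h | 36 h (75%) | 12 h (25%) | 0 h (0%) | 12 h (25%) |

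On the Protocol's clock the latest in-window sample is 192 − 156 = 36 h after the last dose. At 168 h it is 168 − 156 = 12 h after, which is exactly one dosing interval.

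**Sensitivity.**
- Drift in dosing: if dose 14 slips to 162 h or 168 h, the share of the Protocol window with no dose left is 30/48 = 62.5% or 24/48 = 50%.
- Strict calendar days: with Days 6 to 8 and a first dose at clock hour h, the window runs from 120 − h to 192 − h, which is 72 h. The share with no dose left is (36 − h)/72: 50% at midnight, 33% at noon, 18% at 23:00. The share beyond one interval is (24 − h)/72: 33%, 17% and 1%. The SAP row in the table is therefore an approximation.
- Late visits: SAP 6.1.7.2 has a rule for Day 7 visits at 240 h or later, which is at least 240 − 156 = 84 h after dose 14. That rule covers the SSS-AUC only.

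**Size of the effect on concentrations.** The documents give no half-life, so none is claimed. Purely as illustration, assume log-linear decline with a half-life t of 2 to 12 h. Relative to the 12-h value, a sample 24 h after the last dose is 2^(−12/t), or 2% to 50%. At 36 h it is 2^(−24/t), or under 0.1% to 25%. At 168 h on the Protocol's clock the ratio is 1.

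**The case against.** A reader might infer that the Day 7 sample is simply a washout value. The documents do not support that. At 168 h the sample is one full interval after dose 14, and even on the Protocol's clock only half the window is later. The documents never call it a trough, and no trough parameter is planned. This objection stands in full.

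The 75% also depends on the clock. Day 2 falls 12-18 h after the 8-10 h assessment, so at 20-28 h, and Day 3 at no more than 28 + 24 = 52 h. That pattern fits Day N = (N − 1) × 24 h, as does the SAP's calendar rule, and on that reading most of the window precedes dose 14. This stands as a limit on the figure. It does not remove the conflict, because Figure 1 counts from the initial dose and the SAP itself sets the Day 7 SSS at 168 h.

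Pre-dose is itself an instruction, and a site can meet it at 144-156 h even on the literal window. True, but nothing restricts the draw to those hours. The remark in Protocol 10.2.1 about different timing points back to Table 1, which adds no rule.

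SAP 11.1 uses actual elapsed times, but for parameter estimates, which a single Day 7 sample cannot support. They do not govern the time-point summary.

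The consequence is small: sPLA2 is exploratory, by-subject concentrations are also presented, and visit timing does not depend on allocation. Late samples would tend to weaken a Day 7 contrast rather than favour an arm. This also stands.

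**Conclusion.** The label and the window conflict, and the two documents disagree on when Day 7 is. With every interval at 12 h and no missed doses, the share of the window with no dose left is 75% on the Protocol's clock and about 25% on the SAP's. The share more than one interval after the last dose is 50% against about 0%. These are shares of window hours. They become shares of samples only if visits are spread evenly, and the documents do not say how visits will fall.

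Only samples later than one interval after the last dose may be washout values. Their effect on the Day 7 mean cannot be stated without a half-life. Setting values below the quantification limit to 0 would pull the mean down further if late samples are unquantifiable. What is exposed is the Day 7 concentration summary and the exploratory sPLA2 analysis; the primary and key secondary endpoints are untouched. Minor severity, and a cheap improvement.

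**What to change.** **Protocol 10.2.1, 10.3.2.1, Table 1 and Figure 1; SAP 6.1.7.15.** Reconcile the Day 7 definitions for the PK and sPLA2 samples, and state how the draw relates to the dosing schedule. Nothing about dosing needs to change.

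**SAP 11.1 and 8.3.13.** Derive time since last dose for each Day 7 sample. Protocol 9.4 already has sites record administration details and asks discharged subjects to note the date and time of each dose. Summarise Day 7 samples taken within about one dosing interval of the last dose, reporting their time since last dose so that mid-interval draws are visible. Show later samples separately against actual time since last dose. List samples whose last-dose time is unknown.

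**Cost.** Wording in both documents and one derived variable. The SAP part needs no new data and can be settled before database lock. The downside is fewer samples in the Day 7 summary, and dose times after discharge depend on subjects' own records.

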10.3.2.2 Pharmacokinetic Parameters

Standard PK parameters assessed will include measures of the extent of absorption using estimates of the area under the curve (AUC), maximum plasma concentration and rate-of-absorption using the maximum concentration (C_{max}), and the time of C_{max} (T_{max}), respectively.

10.3.2.3 Sample Collection

Samples will be collected at the time points specified in Section 10.3.2.1 and the Schedule of Events (Section 2.2).

Blood

The total amount of blood to be collected will include samples for CBC, renal function tests, liver function test, coagulation profile, and biomarkers, sPLA₂ levels, and plasma drug levels. Blood volumes should be adjusted as necessary for pediatric subjects.

Urine

Mid-stream or catheter urine collected for dipstick urinalysis. Urinalysis should not delay care and should not be obtained by catheter unless patient already being catheterized. Urine should not be collected from a bag, but rather from proximal port.

10.3.3 Safety Variables

Safety will be assessed by evaluating AEs, vital sign measurements, clinical laboratory test results, 12-lead ECGs, physical examination findings, and concomitant medications and therapies.

OPX-PR-01

10.3.3.1 Clinical Laboratory Safety Assessments

10.3.3.1.1 Clinical Laboratory Tests to be Performed

Samples for the following laboratory tests will be collected at the time points indicated in the Schedule of Events (Table 1).

Complete blood White blood cell count including differential, hemoglobin/hematocrit,

count (CBC): platelets

Liver function: Albumin, total and indirect bilirubin, alkaline phosphatase, alanine

aminotransferase, aspartate aminotransferase, LDH

Serum chemistry: Sodium, potassium, chloride, bicarbonate, creatinine, BUN, eGFR

Hemolysis Free hemoglobin, haptoglobin, LDH

Myonecrosis CK

Coagulation: PT, PTT, absolute fibringen, INR

Urinalysis: pH, specific gravity, blood, glucose, protein, ketones

Other: sPLA₂ and biomarkers (CRP, D-dimer)

Serum pregnancy evaluated for subjects of childbearing potential only

test:

Routine laboratory specimens will be analyzed at local laboratories, as specified in the study laboratory manual. A central laboratory will be used for nonstandard assays.

10.3.3.1.2 Evaluation of Clinical Laboratory Values

Each local laboratory will provide the normal ranges of values for the clinical laboratory assessments in this study, and the local ranges will be regarded as the reference ranges on which decisions will be made by each Investigator.

If a laboratory value is out of the reference range, it is not necessarily clinically relevant. The Investigator must evaluate the out-of-range values and record his or her assessment of the clinical relevance in the appropriate eCRF.

All clinical laboratory values that in the Investigator's opinion show clinically relevant or pathological changes during or after termination of treatment must be reported as AEs and followed, as described in Section 11.2.5.

10.3.3.2 Clinical Examinations

10.3.3.2.1 Vital Signs

Vital signs will be assessed and recorded at the timepoints indicated in the Schedule of Events (Table 1) per institutional practice. In addition, body temperature will be measured and recorded every 4 to 8 hours during hospitalization.

Ophirex, Inc.	Confidential
OPX-PR-01	

10.3.3.2.2 Twelve-lead Electrocardiogram

A standard 12-lead ECG will be performed at the timepoints indicated in the Schedule of Events (Table 1) per institutional practice. All ECG recordings will be identified with the subject identification, date, and time of the recording and will be attached to the subject's eCRF.

10.3.3.2.3 Physical Examination

A physical examination will be performed at the timepoints indicated in the Schedule of Events (Table 1) per institutional practice.

10.3.3.2.4 Neurological Assessment

For sedated, endotracheally intubated subjects, a separate neurological assessment will be performed according to Section 10.3.1.7.

10.3.3.3 Adverse Events

The definitions and management of AEs, and any special considerations for AEs, are provided in Section 11.

11 ADVERSE EVENTS

11.1 Definitions

11.1.1 Adverse Events

An AE is defined as any untoward medical occurrence in a patient or clinical investigation subject administered an IP that does not necessarily have a causal relationship with this treatment. An AE can therefore be any unfavorable and unintended sign (including an abnormal laboratory finding, for example), symptom, or disease temporally associated with the use of a medicinal product, whether related to the medicinal product, or not.

Pre-existing diseases or conditions will **not** be considered AEs unless there is an increase in the frequency or severity, or a change in the quality, of the disease or condition. Worsening of a pre-existing condition is considered an AE. Abnormal laboratory values related to liver and renal function that are deemed clinically significant by the investigator will always be considered as AEs if they have worsened from baseline. Any other laboratory values that are judged by the site investigator to be wholly caused by the snakebite envenoming will be regarded as AEs at the discretion of the investigator.

Events that occur in subjects treated with control product (SOC), or during treatment-free periods of the study, are also considered AEs.

11.1.2 Unexpected Adverse Event

An expected AE is one for which the nature or severity is consistent with the known AE profile of the product. For a pre-approval test product, the known information is contained in the IB. For a marketed product, the known information is contained in the current package insert for the product.

An unexpected adverse event (UAE) is one for which the nature or severity of which is not consistent with the applicable product information (e.g., IB for an unapproved IP or package insert/summary of product characteristics for an approved product). For example, hepatic necrosis would be unexpected (greater severity) if the IB only listed elevated hepatic enzymes or hepatitis. Likewise, cerebral vasculitis would be unexpected (greater specificity) if the IB only listed cerebral vascular accidents.

Furthermore, reports that add significant information on specificity or severity of a known, already documented adverse reaction constitute unexpected events. Examples would be (a) acute renal failure as an expected adverse reaction with a subsequent new occurrence of interstitial nephritis (interstitial nephritis would be unexpected) and (b) hepatitis with a first occurrence of fulminant hepatitis (fulminant hepatitis would be unexpected.)

